**Acceptability, Feasibility and Safety of a Yoga Program for Chronic Pain in Sickle Cell Disease**

NCT03694548

Date: Sept 13, 2018

**Title:** Acceptability, Feasibility and Safety of a Yoga Program for Chronic Pain in Sickle Cell Disease

PI: [name], MS

**Abstract:** Chronic Pain is associated with substantial morbidity, functional disability and poor quality of life in patients with Sickle Cell Disease (SCD). The etiology of chronic pain in SCD is multi-factorial. While opioid-based therapy is effective for the treatment of acute pain, opioids and other pharmacological therapies may not be effective in the management of chronic pain and are associated with risks. Complementary therapies, such as yoga, have been demonstrated to be effective in patients with non-SCD chronic pain conditions and may be effective in SCD. Yoga is generally safe and well tolerated, and preliminary evidence in SCD suggests potential efficacy for SCD pain. In-person yoga classes may be prohibitive due to cost and access to these programs may be limited in minority, low-income populations. Smartphone applications available are not tailored to SCD chronic pain. In this study, we propose to study the acceptability, feasibility and safety of yoga for SCD associated chronic pain. Following completion of the study, we also aim to assess participant interest and needs in the development of a smartphone based application for yoga in SCD.

## BACKGROUND AND SIGNIFICANCE:

Chronic persistent pain with recurrent acute exacerbations is a major cause of morbidity, impaired quality of life, healthcare utilization and increased mortality in SCD . Chronic pain in SCD is associated with higher healthcare utilization, increased work absences and greater functional disability  with a negative impact on physical, social and emotional functioning. While opioids are used in the management of chronic pain in SCD, they are associated with substantial risks, there is a need for safe and effective non-pharmacological methods for treatment of SCD chronic pain. Long term opioids are associated with significant risks including pharmacological and psychological dependence, drug interactions, and lethal overdose. Long-term opioid use is also associated with gastrointestinal and endocrine dysfunction, increased risk for cardiovascular events, increased risk for fractures and increased risk for sleep disorders . Use of opioids may paradoxically increase pain sensitivity, a phenomenon termed as opioid induced hyperalgesia.

Mind-body therapies such as yoga can alter pain and related comorbidities. Yoga promotes the relaxation response with decreased heart rate, increased breath volume and improved physiological responses to stress  and pain as well as an increase in parasympathetic activity. Mind-body therapies may decrease the sensory discriminative and affective-motivational aspects of pain even when not engaged in practice. Study of yoga and mindfulness based interventions suggest that these interventions can reduce pain and comorbidities, such as anxiety depression, and fatigue, and multiple investigators have demonstrated the effectiveness of yoga in a variety of chronic pain syndromes such as low- back pain, fibromyalgia, osteoarthritis and chronic neck pain as well as in functional pain syndromes. Use of complementary therapies including mind-body interventions has also reduced opioid use in a small population of patients with chronic pain. The practice of yoga has been attributed to reduced pain, increased coping, better pain acceptance and increased control. There is also decrease in sensitivity to laboratory induced pain with mindfulness meditation-based techniques. Yoga has also been shown to be associated with decreased cortisol , decrease in inflammatory signaling, in autonomous nervous system function with decreased sympathetic and increased parasympathetic system signaling. Pro-inflammatory biomarkers have been reported to be decreased with yoga.

Yoga is the fifth most popular complementary therapy in children and adolescents in the US. SCD chronic pain offers several therapeutic targets that may be responsive to yoga, and limited data in SCD suggests it is well tolerated. SCD chronic pain is associated with psychological comorbidities such as anxiety, depression, fatigue and maladaptive coping, as well as chronic inflammation, all of which may be impacted by yoga. Limited data suggests yoga is well tolerated in children with SCD admitted for acute pain, and a single session was reported to decrease mean pain intensity but not anxiety, length of stay or opioid use.

Lack of awareness and access to yoga are barriers to the use of yoga, and smartphone apps may overcome this barrier. Limited health knowledge is one of the reasons for non-use of complementary therapies, and individuals with lower educational attainment, and lower income were more likely to report lack of knowledge as a reason for non-use of these therapies. There are increased challenges in access to yoga for minority and low-income populations, since yoga is often a fee-based service and there may be additional limitations due to geographical access.

While there is currently no data on the use of yoga as a Complementary and Alternative Medicine (CAM) therapy in SCD chronic pain, one study in acute SCD pain suggest that the practice was well accepted and well tolerated. Additionally, preliminary data from a secondary data analyses of the decision aid study suggests that adult patients express a desire for non-medication based pain relief. These data indicate that patients with SCD who suffer from chronic pain, may be willing to consider CAM therapies. A customized yoga program, taking into account risks of SCD, and limitations posed by SCD-related comorbidities, including but not limited to fixed deformities, AVN, splenomegaly, lung disease, cerebral vasculopathy, retinopathy, etc.

The overarching goal of this study is to 1) determine the acceptability of yoga for chronic pain in SCD 2) determine the feasibility of a yoga program for individuals with SCD chronic pain, 3) determine the safety of a yoga program for individuals with SCD chronic pain, 4) determine the feasibility of collection of psychological and patient reported outcomes in a study of yoga for chronic pain and 5) Explore patient acceptability of yoga through qualitative interviews and conduct a needs assessment for the development of a smartphone app for yoga.

## **AIMS:**

### **Aim 1. Acceptability, feasibility and safety of a yoga program for chronic pain in SCD.**

We will assess the acceptability of yoga for chronic pain in SCD. We will also assess the feasibility and safety of a yoga program for adolescents with SCD and chronic pain.

**Rationale:** Yoga content customized for patients with SCD chronic pain, is currently not available for patients. We propose for the first time to develop routines with consideration of needs, expectations and physical limitations of SCD. The overall acceptability, feasibility and safety of such a program in SCD is yet to be studied, though data from other chronic painful and inflammatory conditions do not suggest safety concerns.

**Hypotheses:** 1a) We hypothesize that more than >50% of those with chronic pain approached to complete a survey of their attitudes and practices related to yoga, would be willing to complete a survey. 1b) At least 50% of adolescent SCD patients with chronic pain offered participation in a yoga program through in-person yoga sessions will agree to participate in the yoga program 1c) At least 80% of participants enrolled in the in-person yoga program will be

able to attend at least 6 of 8 in-person yoga sessions. 1d) Fewer than 30% of participants will have an ED visit or hospitalization for pain within 24 hours of completion of a yoga session.

**Aim 2: Feasibility of collection of psychological and patient-reported outcomes in a study of yoga for chronic pain in SCD.**

**Rationale:** Yoga content tailored and customized for patients with SCD chronic pain, is currently not available for patients. We propose for the first time to develop routines with consideration of individual needs, expectations and physical limitations. In addition to aims in Aim 1, we propose to measure health outcomes and psychological characteristics pre- and post- the yoga program, with a goal to determine the feasibility of collection of these outcomes in a larger study. Since our sample size is small, and this is a pilot feasibility study, it will not be powered to assess measurable benefit (or lack of) from the yoga program, therefore these outcomes will be exploratory. These outcomes will be collected regardless of the number of yoga sessions attended.

**Hypothesis:** 2a) We hypothesize that 70% or more of participants will complete all study assessments before, and at the end of the yoga program. 2b) We hypothesized that the proportion of participants who submit at least 4 days of pain diary data before, and at the end of the yoga program will be 70% or greater.

**Aim 3. Explore patient acceptability of yoga through qualitative interviews and conduct a needs assessment for the development of a smartphone app for yoga.**

**Rationale:** Qualitative Interviews will be used to assess aspects of acceptability and use of yoga as an adjunct therapy for SCD chronic pain. We will also use qualitative interviews format to assess participant interest and perceived needs in the development of a smartphone yoga app. Qualitative thematic analysis methods or other methods as applicable will be utilized.

**Outcome Measures:**

**The study will have the following primary outcome measures:**

- 1- Proportion of adolescent patients with SCD and chronic pain approached that consent to participate in Part A.  
*The study hypothesis is that the proportion of adolescent patients with SCD and chronic pain approached that consent to complete a survey to assess attitudes and practices related to yoga (Part A) will be 50% or greater.*
- 2- Proportion of adolescent patients with SCD and chronic pain enrolled in Part A that consent to participate in Part B.  
*The study hypothesis is that the proportion of adolescent patients with SCD and chronic pain enrolled in Part A that consent to participate in Part B will be 50% or greater.*
- 3- Proportion of participants enrolled in Part B that attend at least 6 of 8 yoga sessions.  
*The study hypothesis is that the proportion of participants enrolled in Part B that attend at least 6 of 8 in-person yoga sessions will be 80 percent or greater.*
- 4- Proportion of participants enrolled in Part B with an ED visit or a hospitalization for pain within 24 hours of completion of each yoga session.

*The study hypothesis is that the proportion of participants enrolled in Part B with an ED visit or a hospitalization for pain within 24 hours of completion of each yoga session will be 30% or less.*

- 5- Proportion of participants in Part B who complete all study assessments.  
*The study hypothesis is that the proportion of participants who complete all study assessments before, and at the end of the yoga program will be 70% or greater.*
- 6- Adherence to submission of pain diary.  
*The study hypothesis is that the proportion of participants who submit at least 4 days of pain diary data before, and at the end of the yoga program will be 70% or greater.*

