**Exclusion Criteria for Group 1 participants:**

- 1- Daytime or nighttime oxygen requirement for hypoxia
- 2- Most Recent Hemoglobin< 5 or platelet count < 20
- 3- Known Pregnancy
- 4- Severe cognitive issues not allowing for understanding consent/assent and instructions
- 5-History of overt stroke with significant residual motor weakness
- 6-History of recurrent syncope
- 7- Any other comorbidities or health concerns that the treating healthcare provider or investigators feel are a contra-indication for participation in the study.

**Inclusion/Exclusion Criteria for Group 2 participants:** There are no specific inclusion/exclusion criteria for parent/guardian participants, except that their child is a participant in the study.

We have developed a survey (attached-Survey Part A) to determine attitudes and practices relating to yoga in patients with SCD chronic pain, and potential acceptability of a yoga program for chronic SCD pain. The presence of chronic pain will be defined based on the based on the frequency characteristic of the AAPT criteria for chronic SCD pain, as the presence of pain on 15 or more days of the month for the past 6 months, and will be determined by self/parent report.

We will also collect the following questionnaires from Group 1 participants in the study: 1) Chronic pain acceptance questionnaire 2) Tampa Scale of Kinesiophobia 3) PROMIS Pain Intensity and Pain interference 4) Pain catastrophizing scale (Crombez et. al.). Surveys may be completed in person, or over the telephone, or may be mailed to participants to complete.

Medical records will be reviewed for pertinent demographic and clinical details including but not limited to those pertaining to SCD, healthcare utilization for pain, other pertinent details about pain phenotype, presence of fixed damage such as AVN, SCD complications, pertinent medical complications, medications, transfusions, and pertinent laboratory values such as (but not limited to) hematological parameters and markers of hemolysis. Since psychological diagnosis are often associated with chronic pain, we will review available psychological and mental health records for co-existing psychological diagnoses. Medical records will also be reviewed for inclusion and exclusion criteria. Note: Only medical records of patient participants (Group 1) will be reviewed; medical records of parent participants (Group 2) will not be reviewed.

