We will also obtain demographic information including but not limited to age, sex, race, ethnicity, family income, insurance status, parent and child education status, family composition and parent marital status, religious affiliation, availability of transportation and distance from the

proposed yoga site. If participants indicate they have previously practiced yoga, we will also gather the following: when yoga was first practiced, number of months/years' yoga has been practiced, frequency of practice and time of most recent practice of yoga. For Group 1 participants, this form may be completed by the parent/guardian for those <18, and by the participant if >18, with or without assistance from the research coordinator. For Group 2 (parent) participants, this will be completed by the parent themselves, with or without assistance from the research coordinator.

At the end of Part A, Group 1 participants will be asked if they are interested in learning about participating a study of yoga for chronic SCD pain. If they answer yes, then they will learn more about the proposed program, and Part B of the study will be offered to them. In addition to the research coordinator discussing the Part B yoga program, we will use written materials to help participants become familiar with what they may expect in part B (attached with this protocol), which will include pictures of sample yoga and breathing routines. Participants may take the Part B consent form with them to think over if they wish to consider this prior to enrolling or refusing participation in Part B. If participants are not interested in a pilot study of yoga or do not wish to enroll/are unable to enroll on Part B, investigators will request and document reason for refusal (if provided), and participant will not have to complete additional study procedures. The proportion of those who complete Part A but do not wish to consent for Part B will be recorded. Group 2 participants will not be offered Part B.

It is anticipated that this introduction and pictures for part B will take approximately 10-15 minutes.

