#### **Recruitment Methods:**

Potential participants will be recruited from Children's Healthcare of Atlanta (Egleston, Scottish Rite and Hughes Spalding locations).

Pre-screening of potential study participants who seek care at CHOA will be done using medical record review. We may also identify patients from the existing SCD clinical database maintained by [name] to identify patients with frequent healthcare utilization for pain or those who potentially may have chronic pain identified through clinical care or prior/ongoing other research studies. This is to limit burden of approaching those patients who are likely to not meet criteria for chronic pain. Participants may also be referred to the study by their treating healthcare providers. If medical records or healthcare provider report/database indicate a possible diagnosis of chronic pain, a research team member will approach the patient/parent to introduce the study and also determine if patient meets eligibility criteria. Patients may be approached for the study either in the inpatient or the outpatient setting. The study staff may also introduce the study in person-or over the telephone to discuss patient interest in the study. If eligible, and the individual is interested, the consent will be reviewed, including expected study activities, and

potential risks and benefits. A copy of the consent may be provided for review based on patient and family preference, either in person or e-mailed/mailed to the potential participant, if so requested. The individual will have an opportunity to discuss it with significant others, including caregivers and other family. The individual will also be given the opportunity to discuss it with his/her hematologist or healthcare provider, if they wish to. This may be done in-person or if the family wishes to, due to time constraints at clinic or hospital visits, over the telephone. Once a potential participant has reviewed consent and all questions have been answered, consent will be obtained in-person.

Specific attention will be given during the consenting process for the potential for increased discomfort and/or pain as a result of the yoga poses. These may result in increased use of medication, or potentially a ED visit, or hospitalization.

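### Could patients who decline before their chronic-pain status is known inflate the Part A consent rate?

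*Combined protocol and SAP*

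**What the plan says.** The first primary outcome, under Outcome Measures, is the "Proportion of adolescent patients with SCD and chronic pain approached that consent to participate in Part A". Its hypothesis is 50% or greater.

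Recruitment Methods describes the approach. Candidates are pre-screened from medical records and a clinical database, or referred by their providers. The stated purpose is: "This is to limit burden of approaching those patients who are likely to not meet criteria for chronic pain". The trigger for contact is worded as a condition: "If medical records or healthcare provider report/database indicate a possible diagnosis of chronic pain". What staff then do at that contact is given in these words: "a research team member will approach the patient/parent to introduce the study and also determine if patient meets eligibility criteria". A further sentence reads: "The study staff may also introduce the study in person-or over the telephone to discuss patient interest in the study". Consent comes afterwards: "If eligible, and the individual is interested, the consent will be reviewed".

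The survey description in Part A, after the Group 1 exclusion criteria, defines chronic pain as "the presence of pain on 15 or more days of the month for the past 6 months, and will be determined by self/parent report".

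For patients who decline Part B, the Part A text asks staff to record a reason if one is offered. It has no matching sentence for patients who decline Part A. Analytic Methods promises descriptive statistics for Part A, and attaches no test, interval or decision rule to outcome 1. No section says how to count an approached patient who leaves before chronic-pain status is established.

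**The concern.** Membership of the denominator depends on a fact that is only suspected when the approach begins. Someone who says no straight away may never supply it. Every consenter, by contrast, has passed the eligibility check. If the analyst counted only patients with confirmed chronic pain, the numerator would stay whole and only non-consenters would be lost. Any error would then favour the 50% hypothesis, on the first-listed primary outcome of an acceptability study. Two analysts following the text could report different rates from the same recruitment. An early refuser's status is also hard to recover later.

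**Working it through.** **Plan's own figure.** The 50% is a hypothesised threshold. There is no sample-size, power or interval calculation for outcome 1, so there is nothing to reproduce.

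**Inputs.** From the documents: at most 40 patients in Part A Group 1 (Total number of participants), the 50% threshold, and eligibility settled before consent review (Recruitment Methods). Not in the documents, and assumed below: the number of refusers, how many are of unknown status, and how many of those have chronic pain.

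**Notation.** C = consenters; R = refusers with confirmed chronic pain; U = refusers of unknown status; k = number of U who truly have chronic pain, from 0 to U.

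- Rate the outcome describes: C/(C+R+k)
- Rate with unknowns left out: C/(C+R)
- Rate with all unknowns counted as refusing: C/(C+R+U)

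**Direction.** Since k is never negative, C/(C+R) is never below C/(C+R+k). The two are equal when k = 0. Leaving unknowns out therefore never lowers the rate, and raises it only if some of them have chronic pain.

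**Size under assumed counts.**

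| C | R | U | Unknowns left out | Half have chronic pain | All have chronic pain |
|---|---|---|---|---|---|
| 40 | 30 | 20 | 40/70 = 57.1% | 40/80 = 50.0% | 40/90 = 44.4% |
| 40 | 20 | 30 | 40/60 = 66.7% | 40/75 = 53.3% | 40/90 = 44.4% |
| 40 | 10 | 20 | 40/50 = 80.0% | 40/60 = 66.7% | 40/70 = 57.1% |

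The described rate falls below 50% only if R + k exceeds C. That needs k = 11 of 20 in the first row and 21 of 30 in the second. It cannot happen in the third, which would need 31 of 20.

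**Break-even in general.** Let p be the rate with all unknowns counted and f the unknown share of all refusals. The rate without unknowns is p/(p + (1−p)(1−f)). Setting this to 0.5 gives f = (1−2p)/(1−p):

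- p = 45%: 0.10/0.55 = 18.2%
- p = 40%: 0.20/0.60 = 33.3%
- p = 35%: 0.30/0.65 = 46.2%
- p = 30%: 0.40/0.70 = 57.1%

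**The alternative convention.** Counting every unknown as refusing is exact only if k = U. In the first row, if k = 0, the described rate is 57.1% and this convention reports 44.4%, which is 12.7 points too low. If k = U, leaving unknowns out is 12.7 points too high. Neither is right in general.

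Nor is the second convention a guaranteed floor if its denominator is approached patients not found ineligible. The outcome's wording is patients with chronic pain, not eligible patients. With C = 40, R = 30, U = 20, all unknowns having chronic pain, and 5 more patients with chronic pain who are excluded for another reason, the literal rate is 40/95 = 42.1%, below 44.4%.

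**Condition on the direction.** The result needs every consenter to be confirmed before consent. If status came only from the survey after consent, and 4 of 40 consenters never supplied it, the confirmed-only rate with R = 30 and k = 0 would be 36/66 = 54.5% against 57.1%, an error the other way. Recruitment Methods does not describe that order, but the self/parent-report sentence does sit in the survey description.

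**The case for a change.** The strongest case for a change is that a pre-specified threshold deserves a pre-specified denominator, that the cost is one sentence and two log columns, and that the rule should be set before recruitment. Pre-screening yields only a possible diagnosis. A tally of approaches, which outcome 1 implies in any case, does not reveal what an early refuser would have answered. In the first row of the table the rule alone decides whether 50% is met.

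Part of this stands. The plan is silent, the direction is as claimed under the order in Recruitment Methods, and recording status at each approach is good practice.

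The rest is weaker. No section adopts the confirmed-only count, so the bias belongs to a rule that the plan does not contain. Establishing eligibility is part of the approach and is named before interest in the consent step. A parent may supply the answer, and records, database and referral narrow the pool beforehand, so the group at issue may be small. The absence of a Part A sentence on reasons for refusal does not show that status will go unrecorded. Finally, the remedy of judging 50% with all unknowns counted as refusing replaces a possible upward error with a possible downward one. Reasonable statisticians would differ on which to prefer.

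**Conclusion.** The concern describes a real silence, but it does not call for a change. It is an unwritten denominator convention in a descriptive pilot, and an analyst can handle it sensibly by giving the number approached, the number of unknown status, and the rate with and without them. Nothing is tested, and no later step depends on outcome 1 reaching 50%.

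The size cannot be derived from the documents. Under the assumed counts, the two conventions differ by 12.7 points in the first row (57.1% against 44.4%) and 22.9 points in the third (80.0% against 57.1%). The conclusion about 50% changes only in cases like the first two rows, and there only if more than half of the unknowns (11 of 20) or more than two thirds (21 of 30) have chronic pain. The direction rests on eligibility being confirmed before consent, and the raised rate on some unknown refusers truly having chronic pain. Fixing one convention in advance would settle which figure is quoted, but would not make that figure more accurate.
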